Study Protocol and Statistical Analysis Plan

Comparison of Surgical Outcomes and Accommodative Changes in Patients With Primary Exotropia Undergoing Medial Rectus Resection-Lateral Rectus Recession and Medial Rectus Plication-Lateral Rectus Recession

Brief Title: Accommodative Changes After Medial Rectus Resection Versus Plication in Primary Exotropia

| | |
|-------------------------------|---|
| Document Type | Study Protocol with Statistical Analysis Plan |
| Document Date | 15 August 2025 |
| NCT Number | Not yet assigned |
| Sponsor | Basaksehir Cam and Sakura City Hospital |
| Study Site | Department of Ophthalmology, Basaksehir Cam and Sakura City Hospital, University of Health Sciences |
| Ethics Approval Number | E-96317027-514.10-236883503 |

1. Study Synopsis

| | |
|----------------------------------|---|
| Study Design | Prospective, interventional, non-randomized, parallel-group comparative clinical study. |
| Population | Patients aged 5 to 40 years with basic primary exotropia eligible for unilateral horizontal strabismus surgery. |
| Study Period | February 2024 to July 2025. |
| Setting | Department of Ophthalmology, Basaksehir Cam and Sakura City Hospital, University of Health Sciences. |
| Allocation | Alternating sequential allocation according to enrollment order; no randomization procedure was used. |
| Intervention Arms | 1) Lateral rectus recession plus medial rectus resection (LRR+MRR). 2) Lateral rectus recession plus medial rectus plication (LRR+MRP). |
| Planned Sample Size | At least 36 patients per group to account for possible loss to follow-up. |
| Final Analysis Population | 85 patients: 40 in the LRR+MRR group and 45 in the LRR+MRP group. |
| Primary Outcome | Change in accommodative amplitude from baseline to postoperative follow-up. |
| Secondary Outcomes | Ocular alignment and surgical success. |
| Follow-up Visits | Postoperative week 1, postoperative month 1, and postoperative month 3. |
| Statistical Software | IBM SPSS Statistics version 28.0. |

2. Background and Rationale

Primary exotropia is a form of horizontal strabismus characterized by outward deviation of one eye. Surgical correction is considered when the deviation is clinically significant, stable, symptomatic, cosmetically concerning, or associated with impaired binocular function. Horizontal strabismus surgery commonly combines weakening of the lateral rectus muscle and strengthening of the medial rectus muscle.

Medial rectus resection has traditionally been used as a strengthening procedure. Medial rectus plication is an alternative strengthening technique in which the muscle is folded and sutured without complete disinsertion from its scleral insertion. Plication may preserve anterior ciliary vessels and adjacent neurovascular structures more effectively than resection. Because the anterior ciliary arteries and related neural pathways contribute to anterior segment physiology and ciliary muscle function, the surgical technique may influence postoperative accommodation.

The purpose of this study is to compare medial rectus resection and medial rectus plication, each combined with lateral rectus recession, with respect to postoperative accommodative changes and surgical outcomes in patients with primary exotropia.

3. Objectives

3.1 Primary Objective

To compare postoperative changes in accommodative amplitude between patients undergoing unilateral lateral rectus recession combined with medial rectus resection and those undergoing unilateral lateral rectus recession combined with medial rectus plication.

3.2 Secondary Objectives

- To compare postoperative ocular alignment between the two surgical groups.
- To compare surgical success at postoperative month 3 between the two surgical groups.
- To evaluate time-dependent changes in accommodative amplitude during postoperative follow-up.

4. Study Design

This is a prospective, interventional, non-randomized, parallel-group comparative clinical study conducted at a single tertiary ophthalmology center. Participants with primary exotropia were assigned to one of two surgical groups. The study compared unilateral lateral rectus recession plus medial rectus resection with unilateral lateral rectus recession plus medial rectus plication.

Participants were allocated using an alternating sequential allocation method according to the order of enrollment. The first participant who consented to participate was assigned to the LRR+MRR group, the second participant was assigned to the LRR+MRP group, and subsequent participants were assigned alternately thereafter. No random sequence generation, allocation concealment, or randomization procedure was used.

5. Study Population

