5.2 Exclusion Criteria

- Spherical refractive error greater than ± 5.00 diopters.
- Cylindrical refractive error greater than ± 3.50 diopters.
- Best-corrected visual acuity worse than 0.1 logMAR.
- Paralytic or restrictive strabismus.
- Previous strabismus surgery.
- Additional ocular pathology, including glaucoma, cataract, uveitis, scleritis, retinal disease, macular disease, or optic neuropathy.
- History of ocular trauma.
- Axial length greater than 26.5 mm.
- Aphakia or pseudophakia.
- High accommodative convergence/accommodation ratio.
- Presence of systemic disease.
- Use of medications known to affect accommodation, including topical pilocarpine, cycloplegics, tricyclic antidepressants, or anticholinergic agents.
- Incomplete ophthalmologic or accommodative examinations.
- Loss to follow-up.

6. Interventions

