8.2 Secondary Outcome Measures

- Ocular alignment: Ocular deviation in primary position was measured using the prism and alternate cover test. Distance and near deviation angles were recorded in prism diopters at baseline and during postoperative follow-up.

- Surgical success: Surgical success was assessed at postoperative month 3 and was defined as ocular deviation in primary position of 10 prism diopters or less of exotropia or 5 prism diopters or less of esotropia.

9. Sample Size

A prior sample size calculation was performed based on the expected between-group difference in operated-eye change in accommodative amplitude from baseline to postoperative week 1, which was considered the primary functional outcome for sample size planning. Assuming a two-sided alpha level of 0.05, 80% power, an anticipated mean difference of 0.7 diopters, and a common standard deviation of 0.97 diopters, the minimum required sample size was estimated to be 31 patients per group. To allow for possible loss to follow-up, at least 36 patients were considered necessary in each group. The final analysis included 85 patients: 40 in the LRR+MRR group and 45 in the LRR+MRP group.

10. Statistical Analysis Plan

All statistical analyses will be performed using IBM SPSS Statistics version 28.0. Continuous variables will be assessed for normality using the Shapiro-Wilk test. Normally distributed continuous variables will be presented as mean \pm standard deviation. Non-normally distributed continuous variables will be presented as median and range. Categorical variables will be presented as number and percentage.

Between-group comparisons of continuous variables will be performed using the Mann-Whitney U test when variables are not normally distributed. Comparisons among more than two independent groups will be performed using the Kruskal-Wallis test. Repeated measurements within groups will be analyzed using the Friedman test. When significant differences are identified in repeated-measure analyses, pairwise comparisons will be performed using the Wilcoxon signed-rank test with Bonferroni correction.

Associations between categorical variables will be evaluated using the Pearson chi-square test or Fisher exact test, as appropriate. A two-sided p value less than 0.05 will be considered statistically significant.

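### The analysed split of 40 LRR+MRR versus 45 LRR+MRP cannot be the split that the stated alternation allocated, and the plan does not account for the difference

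*Combined protocol and SAP*

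**What the plan says.** Section 4 (Study Design) sets a deterministic rule: "Participants were allocated using an alternating sequential allocation method according to the order of enrollment". It fixes the start, "The first participant who consented to participate was assigned to the LRR+MRR group", and the continuation, "the second participant was assigned to the LRR+MRP group, and subsequent participants were assigned alternately thereafter". The synopsis repeats the method: "Alternating sequential allocation according to enrollment order; no randomization procedure was used". Section 4 adds that there was no allocation concealment.

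Section 9 (Sample Size) reports the result: "The final analysis included 85 patients: 40 in the LRR+MRR group and 45 in the LRR+MRP group". The synopsis gives the same counts under the label of final analysis population, not of patients enrolled. The planned size in the synopsis is "At least 36 patients per group to account for possible loss to follow-up".

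Section 5.2 (Exclusion Criteria) includes "Loss to follow-up" and incomplete ophthalmologic or accommodative examinations. Both can remove a patient who has already been allocated.

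No section gives the number enrolled or allocated, the exclusions by arm, or any departures from the sequence. Section 10 does not say whether patients are analysed by the arm due (the arm that their place in the enrolment order assigns) or by the operation received. It also has no method for missing patients.

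**The concern.** The larger analysed group is the arm that the allocation rule can never make larger. Something happened between allocation and analysis, or during allocation itself, that the document does not describe.

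This matters because the sequence was predictable and unconcealed. Keeping to the sequence, and keeping allocated patients in the analysis, is all that protects the comparison from selection. The possible explanations have different consequences. Unequal removal after allocation raises attrition bias. Grouping by operation received makes the comparison as-treated. Departure from the sequence would make the description in Section 4 inaccurate and could admit selection, although a clerical slip would also be a departure. A reader who cannot tell these apart cannot judge the primary comparison.

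**Working it through.** **Inputs.** Alternation with LRR+MRR first (Section 4). Analysed counts 40 and 45 (Section 9 and synopsis). Planning difference 0.7 D, SD 0.97 D, two-sided alpha 0.05, power 80%, 31 per group (Section 9).

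**The plan's own figures.** 40 + 45 = 85, as stated. The sample size also reproduces: 2 × (0.97 × (1.960 + 0.842) / 0.7)² = 30.14, rounded up to 31 per group. Power at 40/45 under the same assumptions is about 91%, so power is not the issue.

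**Split under the rule.** After N allocations, LRR+MRR = N/2 rounded up and LRR+MRP = N/2 rounded down. LRR+MRR minus LRR+MRP is therefore 0 (N even) or +1 (N odd). The analysed difference is 40 − 45 = −5, which no N can give.

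- N = 85: 43 / 42
- N = 90: 45 / 45
- N = 91: 46 / 45
- N = 100: 50 / 50

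**Route 1: rule followed, patients analysed as allocated.** Forty-five analysed in LRR+MRP needs at least 45 allocated there, so N ≥ 90. Let k be the number of LRR+MRP patients removed.

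- N even: 45 + k allocated to each arm. LRR+MRR lost 5 + k, so 5 more.
- N odd: 46 + k and 45 + k allocated. LRR+MRR lost 6 + k, so 6 more.

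Loss rates for some assumed N (two-sided Fisher exact p):

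| N | LRR+MRR removed | LRR+MRP removed | p |
|---|---|---|---|
| 90 | 5/45 (11.1%) | 0/45 | 0.056 |
| 91 | 6/46 (13.0%) | 0/45 | 0.026 |
| 100 | 10/50 (20%) | 5/50 (10%) | 0.26 |

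For even N the difference in rates is 5/(45 + k). It falls from 11.1 points at k = 0 to 10 points at k = 5.

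**Route 2: patients grouped by operation received.** With 85 allocated (43/42) and nobody lost, a net three patients due LRR+MRR but counted in LRR+MRP gives 43 − 3 = 40 and 42 + 3 = 45. No enrolment beyond 85 is needed.

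**Route 3: sequence not followed.** Any split is then possible. The routes can also combine.

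**Possible effect on the estimate (Route 1, N = 90).** Suppose the five missing LRR+MRR patients differ on average by d from the 40 analysed (assumption). The mean over all 45 is the analysed mean plus (5/45) × d. For d = 1 D the shift is 0.11 D, and 0.11/0.7 = 16% of the planning difference. If both arms lost patients, and those patients differ by the same 1 D in the same direction, the shifts partly cancel: at N = 100, 10/50 − 5/50 = 0.10 D.

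**The case against.** The strongest reply is that 40 and 45 are analysed counts and the document labels them so. Section 5.2 allows removal after allocation, so exact alternation followed by unequal exclusion gives 40/45 with no contradiction. This stands. A reader might infer that the figures prove a breach of the allocation rule; they do not.

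Three further points also stand. A reader might take at least 90 enrolled as established, but it holds only if the rule was followed and patients are analysed as allocated; three switches from 43/42 also give the result. A reader might object that enrolment then exceeded the 72 implied by 36 per group, but the plan says at least 36, which is a floor. And 11% against 0% is the case with no LRR+MRP losses, not a minimum difference in loss rates. With losses in both arms the imbalance is readily compatible with chance (p = 0.26 at an assumed N of 100).

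The 0.11 D figure is also modest, since a 1 D average difference exceeds one planning SD (0.97 D).

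It may also be said that participant flow belongs in the publication. That does not answer the point. The document is dated 15 August 2025, after the February 2024 to July 2025 study period, and already reports the final analysis set. The flow counts should be in the enrolment log. Compatibility with chance does not show who left or why, and the missing definition of the analysis set is a gap in the plan itself.

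**Conclusion.** The concern holds in a limited form. It is certain, from the stated rule and the stated counts, that 40/45 is not the allocated split. It follows that LRR+MRR had a net loss of at least 5 relative to LRR+MRP, or some patients are grouped by an operation other than the one due, or the sequence was not followed, or some mixture of these. The documents do not identify which.

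The size depends on the route. In the simplest attrition case, 5/45 against 0/45, the shift is 0.11 D for each 1 D by which the missing patients differ from those analysed. It is smaller if both arms lost similar patients.

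The direction of any bias is also open. Section 2 argues that plication may spare vessels better than resection, and a reader might infer that the missing resection patients had worse accommodation. Nothing in the documents shows who left, when, or with what values. Some may have left before surgery for reasons unrelated to outcome, because assignment is tied to consent.

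**What to change.** 1. Reconcile Section 4 with Section 9 from the enrolment log. Give, per arm, the numbers allocated, operated (by operation due and operation performed) and excluded, with reasons and timing. Counts are enough; a patient-level list is not needed in a public document.
2. In Section 5.2, stop treating loss to follow-up and incomplete postoperative examinations as exclusion criteria. They are missing data. A patient seen at week 1 and lost later still has the value on which Section 9 sized the trial.
3. In Section 10, define the primary analysis set by the arm due under alternation.
4. If the log shows allocated patients missing from the analysis, add a tipping-point analysis: vary the assumed change in accommodative amplitude for the missing patients in each arm and report where the conclusion would change.
5. If the log shows departures from alternation, correct the allocation description in Section 4 and the synopsis, and limit the conclusion accordingly.

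The cost is a review of existing records, some rewording and, if patients are missing, one extra analysis. The downside for the sponsor is that the stated allocation or the completeness of follow-up may look less favourable.

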5.1 Inclusion Criteria

- Patients aged 5 to 40 years.
- Diagnosis of basic primary exotropia.
- Stable deviation angle over three consecutive preoperative visits.
- Deviation angle of at least 20 prism diopters.
- Literacy and cooperation sufficient to perform accommodative amplitude testing.
- Agreement to undergo unilateral horizontal strabismus surgery.
- Written informed consent obtained from the participant and/or legal guardian.

5.2 Exclusion Criteria

- Spherical refractive error greater than ± 5.00 diopters.
- Cylindrical refractive error greater than ± 3.50 diopters.
- Best-corrected visual acuity worse than 0.1 logMAR.
- Paralytic or restrictive strabismus.
- Previous strabismus surgery.
- Additional ocular pathology, including glaucoma, cataract, uveitis, scleritis, retinal disease, macular disease, or optic neuropathy.
- History of ocular trauma.
- Axial length greater than 26.5 mm.
- Aphakia or pseudophakia.
- High accommodative convergence/accommodation ratio.
- Presence of systemic disease.
- Use of medications known to affect accommodation, including topical pilocarpine, cycloplegics, tricyclic antidepressants, or anticholinergic agents.
- Incomplete ophthalmologic or accommodative examinations.
- Loss to follow-up.

6. Interventions

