7.3 Postoperative Follow-up

Follow-up examinations were performed at postoperative week 1, postoperative month 1, and postoperative month 3. At each visit, best-corrected visual acuity, ocular motility, primary position deviation angle, and accommodative amplitude were recorded.

8. Outcome Measures

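### Section 5.2 makes loss to follow-up an exclusion criterion, so the analysis population depends on an event that occurs after allocation and surgery, and no rule keeps partial data

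*Combined protocol and SAP*

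**What the plan says.** - **Section 5.2** places "Loss to follow-up" and "Incomplete ophthalmologic or accommodative examinations" in the same list as baseline criteria such as refractive error and previous surgery. Neither term is defined, and the second has no time point.
- **Section 4** allocates by order of consent: "The first participant who consented to participate was assigned to the LRR+MRR group, the second participant was assigned to the LRR+MRP group". Later patients continue the same strict alternation.
- **Section 7.3** defines follow-up: "Follow-up examinations were performed at postoperative week 1, postoperative month 1, and postoperative month 3".
- **Section 9** bases the sample size on the "operated-eye change in accommodative amplitude from baseline to postoperative week 1, which was considered the primary functional outcome for sample size planning". It arrives at 31 per group and then adds an allowance: "To allow for possible loss to follow-up, at least 36 patients were considered necessary in each group". It reports 85 patients analysed, 40 LRR+MRR and 45 LRR+MRP.
- **Section 10** gives Mann-Whitney for non-normal between-group comparisons. For within-group change it says "Repeated measurements within groups will be analyzed using the Friedman test". It defines no analysis set by allocation and no handling of missing values.
- Section 1 names a single final analysis population. The document nowhere gives the numbers allocated, operated on or excluded in each arm.

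**The concern.** An eligibility criterion has to be decidable before allocation. Loss to follow-up is not: it becomes known only once postoperative visits have been missed. Used as an exclusion, it turns a post-treatment outcome into a condition for being counted.

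Whether a patient returns, or can complete a subjective accommodation test, may depend on discomfort, on the alignment result or on the technique. If so, the patients who remain in the two arms are no longer comparable in the way the alternating sequence was meant to make them. The study has no randomization or concealment, so alternation is its main protection for the group comparison. The month-3 surgical success proportion would have its denominator restricted in the same way.

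There may also be avoidable loss of data. The sample size rests on week 1, yet a patient with a valid week-1 value who later stops attending can meet the exclusion criterion, and nothing in the plan says that the value is kept.

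**Working it through.** **1. The plan's own sample size.** Inputs from Section 9: difference 0.7 D, SD 0.97 D, two-sided alpha 0.05, power 80%.

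n per group = 2 × [0.97 × (1.960 + 0.842) / 0.7]² = 30.14, rounded up to 31. This reproduces the stated figure. The step from 31 to 36 corresponds to an unstated loss of 1 − 31/36 = 13.9%. Losses were therefore expected, but a larger sample protects power and does not remove selection bias.

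**2. Order of events.** Consent and allocation (Section 4), then surgery (Section 6), then visits at week 1, month 1 and month 3 (Section 7.3). Loss to follow-up can only arise in the last stage. The incomplete-examination criterion could refer to the preoperative work-up alone or to any visit; the text does not say.

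**3. What the counts allow.** Strict alternation starting with LRR+MRR means that at allocation n(MRR) equals n(MRP) or n(MRP) + 1. With 40 and 45 analysed:

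removed(MRR) − removed(MRP) = [n(MRR) − 40] − [n(MRP) − 45] = n(MRR) − n(MRP) + 5, which is 5 or 6.

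So, if alternation was followed, at least 5 more patients are missing from LRR+MRR. Two examples:
- 45 + 45 allocated: 5/45 = 11.1% against 0/45.
- 50 + 50 allocated: 10/50 = 20% against 5/50 = 10%.

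**4. Illustrative bias.** If a fraction f of one arm is removed and those patients differ on average by d from the ones retained, that arm's mean shifts by f × d. Take f = 5/45, no removal in the other arm, and d from 0.5 to 1.5 D (assumption; about 0.5 to 1.5 of the planning SD of 0.97 D):
- d = 0.5 D: 0.111 × 0.5 = 0.056 D, and 0.056/0.7 = 8%.
- d = 1.5 D: 0.111 × 1.5 = 0.167 D, and 0.167/0.7 = 24%.

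**5. Power.** Standardized effect 0.7/0.97 = 0.722. A two-sample t-test has 90.7% power at 40/45 and would have 92.3% at 45/45. The precision lost is small.

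**The case against.** Several stronger readings are tempting, and the documents do not support them.

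- *Observed week-1 data were discarded.* A reader might infer this, but no sentence says so. Loss to follow-up is undefined and could mean no postoperative visit at all, in which case there would be no week-1 value to lose. What stands is that such data could be excluded and that no rule protects them.
- *Incomplete examinations were also a postoperative exclusion.* The item sits among baseline criteria, and a preoperative-only reading is natural and unobjectionable. What stands is that the time point needs stating.
- *Five LRR+MRR patients were lost to follow-up.* The excess of 5 follows only if alternation was strict. Departure from the sequence, a change of procedure, or withdrawal between consent and surgery would also produce 40/45, and none of these involves the criterion at issue.
- *The Friedman test removes the same patients from the primary comparison.* Friedman does need every visit, but Section 10 assigns it to change within groups. The week-1 contrast between groups by Mann-Whitney needs only the baseline and week-1 values.
- *The bias could approach half of the planned effect.* With 5 of 45 removed, that would take a difference of about 3 D between removed and retained patients (0.111 × 3 = 0.33 D, 48% of 0.7 D). This is roughly three planning SDs, and nothing in the documents makes it plausible.

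It is also fair to say that both analysed arms exceed 36 and that the document openly declares the absence of randomization. Neither point answers the concern about a criterion applied after treatment.

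**Conclusion.** The point holds, and it should be corrected before the comparison is relied on. Listing loss to follow-up in Section 5.2 is a stated rule, not just a missing detail: it removes allocated and, in this design, operated patients on a post-treatment event, and no analysis set or missing-data rule elsewhere repairs it. This conclusion rests on the text alone and does not depend on the 40/45 split.

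The size of any bias cannot be established from the documents. The range of 0.06 to 0.17 D (8% to 24% of the planned difference) is an illustration under two assumptions: 5 of 45 removed from one arm and none from the other, and a mean difference of 0.5 to 1.5 D between removed and retained patients. The true figure could be smaller or larger, and the direction is unknown. Power is not the issue.

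**What to change.** 1. Delete loss to follow-up from Section 5.2 and limit the incomplete-examination criterion to the preoperative baseline.
2. In Section 10, define the primary analysis set as all allocated patients who had surgery, in their allocated arm, using every available postoperative value. At a minimum, the week-1 contrast should include every patient with a week-1 value. A mixed model over all visits is one suitable way to use partial series; it is not the only one.
3. Report, by arm and with reasons, the numbers allocated, operated on, seen at each visit and excluded. This would also show whether the 40/45 split arose from exclusions or from something else.
4. Keep the completer analysis as a sensitivity analysis.

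The cost is revised SAP wording and some re-analysis, with no new patients or visits. The study period ended in July 2025 and the document is dated 15 August 2025, so rewording alone cannot undo exclusions already made. The documents do not say whether records of excluded patients were kept. Where they were not, the exclusions must be reported by arm as a limitation.
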